- c. Justification and safety information if non-FDA approved drugs without an IND will be administered. N/A

7. Study Statistics

- a. Primary outcome variable.

Change in performance from baseline to 1st post treatment on Penn CNB tasks (Total) vs. 1st post-treatment (new baseline) to 2nd post-treatment on Penn CNB tasks (total).

- b. Secondary outcome variables.

Changes in total and subtest scores on IRI, Prosody Battery, RMET, Faux Pas Test, and star cancellation.

- c. Statistical plan including sample size justification and interim data analysis.

We will compare the change in means of outcome measures after social cognition treatment vs. control treatment. The primary outcome variable will be change in performance on the Penn CNB tasks after the end of each treatment. The null hypothesis is $H_0: \mu_1 = \mu_2$, where μ_1 is the mean change in performance on the Penn CNB tasks between pre-treatment and post-treatment with social cognition treatment and μ_2 is the mean performance on the Penn CNB tasks between pre-treatment and post-treatment with control treatment.

Analyses. In a cross-over trial, it is essential to evaluate the effect of condition versus the effect of sequence of the treatment, and to evaluate for carry-over from one treatment to the next. Based on our clinical experience we expect little change in the Penn CNB with the control (non-specific cognitive exercises) in chronic right hemisphere stroke (as we see decline rather than recovery in chronic stroke in these functions), and little change or decline in patients with behavioral variant FTD. But we will evaluate the effect of condition versus sequence independently. The primary analyses will evaluate the change in performance on Penn CNB as the dependent variable, $Y_{ij} = \mu + S_i + \mu_{(j)} + C_{(j)} + e_{ij}$ where i represents a subjects, j represents the sequence (1 or 2). The Y_{ij} is the change in the evaluations. The S_i represents the random effect of the subjects. The $\mu_{(j)}$ represents the means of the two treatments (social cognition or control). The $C_{(j)}$ represents the carryover effects. The test for the treatment effect can be obtained from this model. Firstly, the effect of carryover effects will be tested at $p < 0.1$. If this is significant, then only the first sequence data will be analyzed as this sequence is free of carryover effects. A similar analysis will be done for the change in accuracy of secondary outcome variables.

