Power. We expect to enroll up to 50 patients in the study, and expect 20-30 participants will complete the study. Because of the social cognitive deficits in these patients (accompanied by relatively low insight and motivation), there is likely to be high attrition. If the sample size in each treatment group is 13, (a total sample size of 26) a crossover design will have 86% power to detect a difference in means of 6 (the difference between treatment mean change in accuracy, μ_1 , of 10 and a control mean change in accuracy, μ_2 , of 4) using a two group t -test with a two-sided alpha of 0.05.

- d. Early stopping rules.

Patients will be allowed to stop at any time, but they will not receive compensation if they fail to complete all criteria for compensation. Their data will only be used for Aim 1 if they complete the entire study. We may be able to use data from participants who complete the social-cognition treatment condition only for Aims 2 and 3.

8. Risks

- a. Medical risks, listing all procedures, their major and minor risks and expected frequency. There are no known risks associated with the training software, use of a laptop computer, or the assessments used in this study. Participants could become bored, anxious, or embarrassed during assessment of cognitive function.
- b. Steps taken to minimize the risks. The participant will be able to stop participation at any time if they experience any issues with the use of the training software or assessments of social abilities.
- c. Plan for reporting unanticipated problems or study deviations. The PI will report unanticipated problems or study deviations to the IRB immediately.

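### Section 7c takes the treatment test from a model that includes carryover and gives no reduced model; under first-order coding this loses the within-patient comparison

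*Combined protocol and SAP*

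**What the plan says.** Section 7c (Analyses) writes the change in the Penn CNB total as the sum of an overall mean, a patient effect, a treatment mean, a carryover term and error. Of these terms it says "The S_i represents the random effect of the subjects" and "The $C_{(j)}$ represents the carryover effects". The index is introduced only by "j represents the sequence (1 or 2", closing the bracket. There is no separate period term, and no statement of how C enters in each period or order.

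On the treatment test: "The test for the treatment effect can be obtained from this model". Carryover is tested first, at the 0.1 level, and then: "If this is significant, then only the first sequence data will be analyzed as this sequence is free of carryover effects". No action is stated for a non-significant carryover test, and no model without C is given. The same approach is applied to the secondary outcomes.

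The Power paragraph of 7c states that "a crossover design will have 86% power to detect a difference in means of 6", with 13 per group (26 in total), mean changes of 10 and 4, a two-group t-test and a two-sided alpha of 0.05. It gives no SD and no within-patient correlation. The Abstract (section 1) describes a crossover in which patients are their own controls.

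**The concern.** In a design with two orders and two periods there are only two between-order contrasts, one per period. If the model spends one of them on carryover, a single contrast is left for treatment, and that is the first-period comparison of about 13 v 13. An analyst who follows 7c to the letter, with C entered as a first-order carryover effect, would then get the same between-patient estimate whether or not the carryover test was significant. The second-period data would add nothing to the primary estimate.

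At stake is the sole primary test, in a trial that expects 20-30 completers. Because the coding is not written down, two analysts could also take different primary estimates from the same data.

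**Working it through.** **Inputs.** From 7c: 13 per group, 26 in total; difference 10 - 4 = 6; two-sided alpha 0.05; power 86%. Assumed, because the documents do not give it: the correlation rho between a patient's two change scores, shown at -0.5, 0 and +0.5. Write s for the SD of one change score.

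**1. The stated 86%.** With no SD it cannot be reproduced forward, so it is solved backward. For a t-test with 24 df, 86% power needs a noncentrality of 3.169. Two readings fit equally well:
- Crossover, SE = SD of within-patient difference / √26: SD = 6 × √26 / 3.169 = 30.59 / 3.169 = 9.65.
- Parallel 13 v 13, SE = SD of change × √(2/13): SD = 6 × √6.5 / 3.169 = 15.30 / 3.169 = 4.83.

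(The normal approximation gives 10.06 and 5.03.)

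**2. The estimate with first-order carryover kept.** Let T be the treatment effect and L the difference in carryover between the two conditions. The expected difference, social-first minus control-first, is:
- period 1: T
- period 2: -T + L

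L appears only in the second line and fits it exactly, so T is estimated from the first line alone.

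**3. Other codings.** Generalised least squares on the four cell means gives these treatment weights, in the order social-first period 1, social-first period 2, control-first period 1, control-first period 2:

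| Coding of C | Weights | Comparison |
|---|---|---|
| First-order carryover, with or without a period term | 1, 0, -1, 0 | First period only |
| Sequence-group effect | 0.5, -0.5, -0.5, 0.5 | Within-patient |
| One common second-period effect | 0.5, -0.5, -0.5, 0.5 | Within-patient |
| Carryover from the social condition only, no period term (rho = 0) | 0.5, 0, -1, 0.5 | Intermediate |

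In the intermediate case the variance at rho = 0 is 0.75 of the first-period variance. Adding a period term returns the weights to 1, 0, -1, 0.

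**4. Loss under first-order coding.** Variance with C = 2s²/13 = 0.154s². Variance without C (patient, period, condition) = (1 - rho)s²/13. The ratio is 2/(1 - rho). For power, take the 86% as a crossover figure, so s = 9.653/√(2(1 - rho)) and first-period SE = s√(2/13), with 24 df:

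| rho | Variance without C (× s²) | Ratio | s | First-period SE | 6/SE | Power, 13 v 13 | Total completers for 86% |
|---|---|---|---|---|---|---|---|
| -0.5 | 0.115 | 1.33 | 5.57 | 2.19 | 2.74 | 75% | 34 |
| 0 | 0.077 | 2 | 6.83 | 2.68 | 2.24 | 58% | 50 |
| +0.5 | 0.038 | 4 | 9.65 | 3.79 | 1.58 | 33% | 98 |

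If the 86% was a parallel calculation (s = 4.83), first-period power is 86% already.

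**5. Which rho is plausible.** Section 7a makes the mid-study score the end of the first change and the start of the second. Let e² be the error variance at each visit and v the between-patient variance in slope. Then rho = (v - e²)/(v + 2e²). With v = 0 this is -0.5. Reaching 0 needs v = e², and reaching +0.5 needs v = 4e².

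**The case against.** A reader might infer that the plan discards the second period outright, so that no patient ever acts as their own control and the crossover precision behind the 86% is never used. The documents do not support that, for three reasons.

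First, the result depends on a coding that 7c does not give, and two codings open to its notation keep the comparison fully within-patient. This stands, though the text leans toward first-order carryover. It speaks of an effect passing between treatments, and it treats the first *sequence* as untouched by carryover. That describes a period, and a sequence-group effect would be present in both periods. The treatment mean has the same index as C, which suggests that C also depends on treatment.

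Second, restricting the analysis to first-period data when carryover is significant makes sense only if both periods are used otherwise. Section 7d also limits Aim 1 to patients who complete the whole study. This stands as evidence of intent. It does not supply the missing model.

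Third, the 86% cannot be tied to within-patient precision. The paragraph names a crossover, but also a two-group t-test with 13 in each treatment group, and both back-solved SDs fit. This stands, so the fall in power is conditional.

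The shared mid-study score also makes the 33% figure the less likely end of the range. The error rate of the two-stage procedure is a separate question, although it arises from the same sentences.

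**Conclusion.** The point holds as a gap in specification with a conditional consequence. Section 7c does not define how C is coded, does not separate period from order, and does not say that C leaves the model when its test is not significant. Under the coding that fits the text best, keeping C reduces the treatment estimate to the first-period difference, and the within-patient comparison described in the Abstract is lost. The variance is then 1.33 to 4 times that without C for rho from -0.5 to +0.5, with the lower end more plausible.

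Power falls to about 75%, 58% or 33% only if the 86% is a crossover figure with an SD of the within-patient difference near 9.65. If it came from a parallel calculation with an SD of change near 4.83, power stays at the stated figure and the crossover label is what is wrong. Rho and both SDs are assumed or back-solved; none is in the documents.

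**What to change.** In 7c:
- Define period (first or second) and order (social-first or control-first) as separate terms.
- Take the primary treatment test from both periods, in a model with patient, period and condition and without C, whatever the carryover result.
- Report the carryover estimate with its confidence interval from a separate model, as a sensitivity analysis.
- State the SD behind the 86%, and whether it is the SD of a change or of a within-patient difference.
- If C is kept in the treatment test, restate the power for a first-period comparison of 13 v 13.

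The cost is wording only; no visit or measurement changes. The downside is that without C the estimate assumes equal carryover in the two orders, and the report must say so. Keeping C avoids that assumption, but at the lower precision shown above under first-order coding.

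### Section 7c lets a carryover pre-test at p<0.1 choose the primary analysis; on the usual two-step reading, which the text does not fully state, null error is about 6-8% rather than 5%

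*Combined protocol and SAP*

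**What the plan says.** Section 7a defines the primary outcome as the Penn CNB change over the first training block set against the change over the second, the latter measured from "1st post-treatment (new baseline) to 2nd post-treatment on Penn CNB tasks (total").

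The Analyses paragraph of section 7c gives a model for the change scores with a subject effect ("The S_i represents the random effect of the subjects"), a treatment mean and a carryover term. No period term is listed. On the treatment comparison it says: "The test for the treatment effect can be obtained from this model". The order of testing follows: "Firstly, the effect of carryover effects will be tested at $p < 0.1", and then "If this is significant, then only the first sequence data will be analyzed as this sequence is free of carryover effects". For the other endpoints: "A similar analysis will be done for the change in accuracy of secondary outcome variables".

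The only significance level given for the treatment comparison is in the Power paragraph of section 7c: "using a two group t -test with a two-sided alpha of 0.05". That paragraph assumes 13 per group, and the investigators "expect 20-30 participants will complete the study".

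The plan does not define the contrast that tests carryover. It does not say whether the carryover term leaves the model when it is not significant, and it gives no SD and no correlation between the two changes. Section 4a describes no washout between the two training blocks.

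**The concern.** A carryover test in a two-period crossover compares the two orders on their totals over both periods. The fallback compares the same two orders on the first period alone. Both statistics contain the first-period data, so a chance first-period imbalance makes the switch more likely and also pushes the fallback test towards significance. Each test has its nominal level when it stands alone, but the rule that chooses between them does not.

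What is at stake is the error rate of the primary test and, because the same rule is extended to them, of the tests on the secondary outcomes. The excess falls entirely in trials that would report the fallback result. The rule also costs power when there is no carryover. Nor does a non-significant pre-test show that carryover is absent, because a test on between-patient totals with about 13 per order is weak.

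**Working it through.** **Inputs from the plan.** Pre-test level 0.10 (taken as two-sided), treatment test two-sided 0.05, 13 per order, 20-30 completers (10-15 per order), mean changes 10 and 4.

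**Assumed.** Normal change scores c1 and c2 with equal variance and correlation rho = -0.5, 0 or +0.5. The documents point both ways on rho. The two changes share the middle assessment: with three equally variable, equally correlated assessments (correlation r), cov(c1,c2) = -(1-r)σ² and var(c) = 2(1-r)σ², so rho = -0.5. A random subject effect on the change scores instead implies rho of 0 or above.

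**Reading.**
1. The fallback uses first-period data, since only those can be free of carryover.
2. Carryover is tested by a two-sample t-test of c1+c2 between orders.
3. If that is not significant, treatment is tested on c1-c2 between orders. If it is significant, treatment is tested on c1.

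**The plan's 86% power.** It cannot be confirmed without an SD, so I solved for one. A two-group t-test needs SD 4.83 per change score: 6/(4.83×√(2/13)) = 3.17 on 24 df, giving 86%. A within-patient contrast needs an SD of 9.65 for c1-c2: 6×√26/9.65 = 3.17, again 86%. The second corresponds to 9.65/√(2(1-rho)) = 5.57, 6.83 or 9.65 per change score.

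**Null error, large-sample check.** The sum and difference are independent, so the non-significant branch contributes 0.90×0.05 = 0.045. The pre-test and first-period statistics have correlation √((1+rho)/2) = 0.50, 0.71 or 0.87. The probability that both are significant is 0.0148, 0.0251 or 0.0370. The totals are 0.060, 0.070 and 0.082.

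**Null error by simulation with t-tests, no carryover.**

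| | rho -0.5 | rho 0 | rho +0.5 |
|---|---|---|---|
| Fallback triggered | 10% | 10% | 10% |
| Two-step error, 13 per order | 6.0% | 6.9% | 8.1% |
| Two-step error, 10 per order | 5.9% | 6.9% | 8.0% |
| Two-step error, 15 per order | 5.9% | 7.0% | 8.1% |
| Error given the fallback, 13 per order | 14% | 24% | 36% |
| Crossover or first-period test alone | 5% | 5% | 5% |

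**Carryover term kept in both branches.** With a period term, or a separate carryover term for each preceding condition, the treatment estimate is the first-period contrast either way. Simulated error is 5.0-5.1%.

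**Power at 10 vs 4, no carryover, 13 per order.** With SD 9.65 for c1-c2, the crossover contrast has 86%, the two-step rule 84%, 83% and 82%, and the first-period comparison, unadjusted for baseline, 75%, 58% and 33%. With SD 4.83 per change score, the first-period comparison itself has 86%, the crossover contrast 94%, 99% and 100%, and the two-step rule 93%, 96% and 96%.

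**If first-period gains fade (true difference 6).**
- Half of each gain fades. Social-first changes are 10 and 4-5 = -1; control-first changes are 4 and 10-2 = 8. The crossover contrast estimates [(10+1)-(4-8)]/2 = 7.5. The two-step rule averages 6.5-6.8.
- Half of the social gain only fades. Changes are 10, -1 and 4, 10. The crossover contrast estimates [(10+1)-(4-10)]/2 = 8.5. The two-step rule averages 6.2-7.2. The pre-test triggers in 72%, 36% and 19% of trials with SD 9.65 for c1-c2, and in 82%, 57% and 44% with SD 4.83 per change score.

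**The case against.** The strongest reply is that the inflation depends on readings the text does not give. Section 7c says the treatment test comes from the displayed model, and that model contains the carryover term. If the term is always kept, error is about 5%. That is correct, and it stands as a limit on the claim. But the treatment estimate would then be the first-period contrast whatever the pre-test showed, and the written fallback would change nothing. Dropping the term is the reading that gives the rule a purpose.

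A second reply is that the carryover term, as printed, is indexed only by what the plan calls sequence. If that means period, the pre-test would be on a period-level term, and simulated two-step error is 4.8-5.0%. But a period-level term is not a carryover effect, and testing it would not serve the stated aim of finding data free of carryover. The ambiguity in the notation is real and should be removed.

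A third reply is that the excess is modest and rests on an assumed correlation. Both points stand: it is 1 to 3 percentage points. A reader might take the 14-36% as the trial's false-positive rate. It is not. It applies only to the 10% of null trials that trigger the fallback, and it is already counted in the 6-8%.

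A fourth reply is that the pre-test gives some protection, so removing it could make matters worse. This also stands in part. In the fading scenarios the crossover contrast alone is more biased than the two-step rule.

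**Conclusion.** The point holds in a conditional form. It is certain from the text that a carryover test at p<0.1 selects the primary analysis, that no adjustment is made, and that the carryover contrast and the non-significant branch are not fully specified. On the usual two-step reading, null error is about 6%, 7% or 8% for assumed correlations of -0.5, 0 or +0.5, and power without carryover is 2 to 4 points below the crossover contrast. If the carryover term is always retained, error is about 5% and the fallback is redundant. Section 7c needs rewording on either reading.

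Two stronger inferences are not supported. The first is that the trial's error rate is established as above 5%: the documents give neither the correlation nor two of the readings on which the figure rests. The second is that the crossover contrast alone would be safer: without a washout it gives 7.5-8.5 for a true 6 when gains fade as above. The point deserves correction before analysis, but the excess error is modest.

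**What to change.** Remove the data-driven switch from section 7c. Name one primary analysis in advance at two-sided 0.05 and give the reason for it:

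- the crossover contrast with a period term, if the team can defend little or no carryover without a washout; or
- the first-period comparison adjusted for baseline Penn CNB, if it cannot.

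Whatever the carryover result, report the other treatment estimate and the carryover estimate with 95% confidence intervals as descriptive sensitivity results. Define the carryover contrast explicitly. Do not attach a label saying that a result is robust to carryover. A label based on the first-period estimate agreeing in direction and its interval covering the crossover estimate would still be met in 78-94% of trials in which half the social gain fades, so it would reassure without discriminating. Apply the same rule to the secondary outcomes.

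**Cost.** Choosing the crossover contrast needs new wording in section 7c only, but accepts the bias shown above if first-period gains fade. Choosing the first-period comparison keeps 5% error, but its power before baseline adjustment is 33-75% if the stated 86% refers to the within-patient contrast (86% if it refers to a two-group test with SD 4.83). It also means rewording the outcome definition in section 7a, the abstract's statement on within-patient control and the power paragraph, and possibly revisiting the sample size.

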The proposed study utilizes the PI's experience in speech-language pathology and cognitive neuropsychology, clinical training in neurology, and expertise in dementia to test the effectiveness of web-based social-cognitive training organizations in FTD and right hemisphere stroke. The investigation will focus on characterizing each individual patient's deficits and determining whether cognitive training improves their performance on social-cognitive tasks. The training follows a drill-and-practice bottom-up model that uses principles of neuroplasticity to build and strengthen empathic skills such as prosody identification and facial expression recognition. The design is a cross-over trial, with randomized order of conditions; each participant will serve as their own control. Every participant will engage in both a social-cognitive training condition and a non-specific control training condition in a random order. They will be assessed at baseline, after completing one condition, and after completing the second condition. We hope to identify specific social cognition domains that are influenced by treatment and to characterize what types of patients (e.g. based on lesion location or severity of disease progression) who can benefit from these exercises.

The importance of the results is to provide a potentially effective and low cost treatment for social-emotional impairments in patients with FTD and stroke. Currently there are almost no interventions available for these symptoms in these populations, and if this treatment proves to be effective, it could have major clinical implications for the prognosis and functional outcome

of patients with stroke or FTD. The scientific impact of these results could provide greater understanding of the brain's ability to reorganize and repair damaged empathic networks in the context of training. This mode of training has not been attempted in FTD previously and previous studies of training platforms have primarily focused on language or non-social deficits in stroke. This study will be one of the first in this domain and will elucidate the nature and malleability of the social-emotional impairments in stroke and FTD.

2. Objectives (include all primary and secondary objectives)

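### Aim 1 keeps only people who finish both periods, so the randomised first-period result of anyone who leaves after the first reassessment is discarded

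*Combined protocol and SAP*

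**What the plan says.** Section 7d fixes the analysis set for the efficacy comparison (objective 1): "Their data will only be used for Aim 1 if they complete the entire study". The only other use it offers for incomplete data is a possible one, in Aims 2 and 3, for people who completed the social-cognition condition. Someone who did the control condition first and then left is given no use. No all-randomised analysis set, missing-data method or sensitivity analysis appears elsewhere.

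Section 7c, Power, expects substantial loss: "We expect to enroll up to 50 patients in the study, and expect 20-30 participants will complete the study". It gives the reason: "Because of the social cognitive deficits in these patients (accompanied by relatively low insight and motivation), there is likely to be high attrition".

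The timing of assessments is set in the Abstract: "They will be assessed at baseline, after completing one condition, and after completing the second condition". Section 4a agrees, and has the first condition chosen at random from 30 sealed envelopes.

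The primary outcome (7a) is: "Change in performance from baseline to 1st post treatment on Penn CNB tasks (Total) vs. 1st post-treatment (new baseline) to 2nd post-treatment". The model in 7c has a subject term: "The S_i represents the random effect of the subjects". Carryover is tested at p < 0.1, and 7c then says: "If this is significant, then only the first sequence data will be analyzed as this sequence is free of carryover effects". I read first sequence there as first period.

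**The concern.** A person who leaves after the first reassessment has a baseline score, a randomly assigned condition and a post-treatment score. That is a complete first-period observation and the first half of the primary outcome. Section 7d removes it from Aim 1 because of something that happens later.

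The effect is clearest in the fallback. Once carryover is declared, the analysis is a parallel-group randomised comparison of first-period changes. Under 7d, entry to that comparison depends on finishing a second period that the comparison ignores. Two things are at stake: precision, and the protection that randomisation gives to the first-period contrast if the two orders lose different kinds of people.

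**Working it through.** **Inputs.** From 7c: 13 per group, 26 in total, difference 6 (10 against 4), two-sided alpha 0.05, power 86%, up to 50 enrolled, 20-30 completing. From 4a: 30 envelopes. Not given: an SD, the correlation r between a person's two changes, and the number leaving after the first reassessment.

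**The plan's figure.** Section 7c states: "If the sample size in each treatment group is 13, (a total sample size of 26) a crossover design will have 86% power". With no SD it cannot be reproduced forwards. Solving backwards with the noncentral t on 24 df, 86% power for 6 points needs SE = 1.893. Two readings follow.
- Crossover: SD of the within-person difference between changes = 1.893 × √26 = 9.65. The SD of one change is 9.65/√(2(1 − r)): 5.57, 6.83 and 9.65 at r = −0.5, 0 and +0.5.
- Two-group t-test taken literally: SD of one change = 1.893/√(2/13) = 4.83.

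Negative r is the more plausible case, because the middle score ends the first change and starts the second. If the three scores had equal, independent errors and nothing else varied, r would be −σ²/(2σ²) = −0.5.

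**How many people.** If each envelope is used once, 30 are randomised. Losses are then at most 30 − 26 = 4, or 30 − 20 = 10 at the lower end of the plan's range. Both are upper limits, since some of these people will leave during the first condition. The documents do not say whether envelopes are replenished. A loss of 12 alongside 26 completers needs 38 randomised and is an assumption.

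**Crossover precision.** With N completers and k first-period-only people, split evenly by order, and with treatment and period in the model, the information on treatment is N/(2σ²(1 − r)) + k/(4σ²). The SE is therefore multiplied by 1/√(1 + k(1 − r)/(2N)).

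| N = 26, k = 4 | r = −0.5 | r = 0 | r = +0.5 |
|---|---|---|---|
| 1 + k(1 − r)/(2N) | 1.115 | 1.077 | 1.038 |
| SE (from 1.893) | 1.793 | 1.824 | 1.858 |
| Reduction | 5.3% | 3.6% | 1.9% |
| Power, 24 df | 89% | 88% | 87% |

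These treat the covariance as known. When an unstructured covariance was estimated by REML in simulation, the reductions were about 3%, 1% and 0%, so the table is an upper limit. If the plan's random-subject term is kept (its correlation cannot go below 0) while the true r is −0.5, the SE still falls by 4.8%. Most of the gain therefore needs no change to the covariance in 7c.

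**First-period fallback.** SE = SD × √(2/n), with n per order and 2n − 2 df. Going from 13 to 15 per order multiplies the SE by √(13/15) = 0.93; going from 10 to 15 multiplies it by √(10/15) = 0.82.

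| Fallback power | 10 per order | 13 per order | 15 per order |
|---|---|---|---|
| r = −0.5 (SD 5.57) | 63% | 75% | 81% |
| r = 0 (SD 6.83) | 46% | 58% | 64% |
| r = +0.5 (SD 9.65) | 26% | 33% | 38% |
| Literal two-group (SD 4.83) | 75% | 86% | 91% |

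**Bias.** Simulation with no true effect, r = −0.5, and completion depending on first-period gain in one order only (log-odds slope 0.5 to 1.5 per SD).
- With 4 of 30 lost, the completers-only crossover estimate is off by about 0.3-0.7 points, in either direction. At this r the crossover bias is (1 − r)/2 = 0.75 of the first-period bias, so the fallback is off by about 0.4-0.9 (0.3/0.75 to 0.7/0.75).
- With 12 of 38 lost, the figures are 0.6-1.5 for the crossover and 0.8-2.0 for the first period. Losing 10 of 30 is a similar fraction (33% against 32%), so bias of that order would be expected there.
- If dropout depends on gain equally in both orders, the crossover bias is about 0.

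**The case against.** The strongest defence is that this is a within-person design. Section 7a contrasts two changes in the same person, a one-period participant has no such contrast, and the sample size already counts completers. That makes completers-only a reasonable supporting analysis. It does not justify the fallback, where no within-person contrast is used and the second period plays no part.

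Other points stand and limit the concern. The gain may be zero. The larger benefit sits in a fallback that runs only if the carryover test is significant. On the literal two-group reading, crossover power with 26 completers is already 94% or more, so little is left to gain there. The bias figures are hypothetical, and the simulated dropout depends only on observed first-period gain, which is the condition the recommended analysis relies on.

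A reader might infer more than the documents support:
- That 7d contradicts the fallback. It does not; the fallback can be run on completers.
- That the efficacy estimate is biased. The plan attributes attrition to patient traits, which randomisation should balance, so it leans towards the mild case.
- That the 86% power is overstated. It is set at 26, inside the expected 20-30 completers.
- That 40-60% of usable data are thrown away. That is non-completion if all 50 enrol, and it includes people who never reach the first reassessment.

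**Conclusion.** The concern holds as a cheap improvement. Section 7d states a rule, nothing reverses it, and it discards randomised outcome data that the planned analyses can use. If the envelopes cap randomisation at 30, the effect on the crossover analysis with 26 completers is small. The effect on the fallback is moderate, and larger at 20 completers. These sizes rest on an SD solved from the 86%, an assumed r, and every non-completer leaving after the first reassessment, so they are ceilings. Bias remains a possibility rather than a finding. Confidence is high on the reading of 7d and much lower on the size.

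**What to change.** In 7d, replace the completion rule for Aim 1. Include every randomised participant with a baseline and at least one post-treatment Penn CNB in the planned random-subject model, in the order assigned, and use all first-period data in any first-period-only analysis. Keep completers-only as a sensitivity analysis, and report dropout by order and period so that readers can judge whether the orders differ.

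No change to the 7c covariance is required. A model allowing negative covariance between the two changes can be a further sensitivity analysis: with 12 lost and dropout tied to gain in one order, fixing the correlation at 0 left 0.16-0.40 points of bias.

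The cost is a few sentences and slightly more analysis work; the first reassessment is already scheduled, so no new data are needed. The analysis relies on dropout being explained by observed data. It does not recover people who leave during the first condition, and if most attrition happens there it gains almost nothing.
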